5.2 Continuous Infusion Rate Adjustments

OCR-002 will be infused intravenously (IV) for up to 5 days (0 to 120 h). The Dosing regimen for Cohorts 1 and 2 is as follows:

Dose Level 1: Patients will receive the initial infusion of study drug at 0.139 g/h for the first 12 h (approximately 3.33 g/24h) and maintained at this rate for up to 120h.

Dose Level 2: Patients will receive an initial infusion of study drug at a dose of 0.139 g/h for the first 12 hours (approximately 3.33 g/24h). The dose will be increased to 0.277 g/h for the next 108h (approximately 6.65 g/24h), and maintained at this rate for the remaining treatment period, provided the previous dose level is well- tolerated with no noteworthy side effects and no safety signals are apparent.

Dose Level 3: Patients will receive an initial infusion of study drug at a dose of 0.139 g/h for the first 12 h (approximately 3.33 g/24h). The dose will be increased to 0.277 g/h for the next 12 hours, and then increased to 0.416 g/h (approximately 10 g/24h) and maintained at this rate

for the remaining treatment period, provided previous dose levels are well-tolerated with no noteworthy side effects and no safety signals are apparent.

Dose Level 4: Patients will receive an infusion of study drug at a dose of 20g/24h from initiation of infusion for a maximum time of 120 hours, provided the dose level is well tolerated with no noteworthy side effects and no safety signals are apparent.

If a patient experiences CTCAE grade 1 or 2 adverse reactions or intolerance to the assigned dose, the investigator may choose to titrate to a lower dose in 5g increments and closely monitor the patient. The infusion rate and dose may be discontinued if the patient experiences CTCAE grade 3 or higher, or any time at the investigator's discretion. (See Section 9.7 of the protocol for details on safety review, dose escalation and trial stopping criteria.)

6 PATIENT POPULATION

6.1 Number of Sites and Patients

The study will be conducted at between 6 to 12 centers in the US that are experienced, high-volume sites in the ALF Study Group. All patients enrolled in the therapy trial will have been enrolled in the ALFSG registry. Up to 36 evaluable male and female patients aged 18 to 65 years with ALI/ALF will be enrolled into two cohorts. Each patient may participate in only one cohort. For each patient, the study duration will be approximately 32 days, including Screening, Baseline, up to 5 days of treatment, the Completion of the Last Infusion, a 24 hours Following the Completion of the Last Infusion, and a post treatment period on Day 30 (approximately 30 days after Treatment Day 1-T0 unless terminated early from the trial).

6.2 Selection Criteria

6.2.1 Inclusion Criteria

1. Men and women, ages 18-65 (have not reached their 66th birthday).
2. Acute liver failure, defined as the development of coagulopathy (International normalized ratio [INR] ≥ 1.5) with encephalopathy in a patient with no prior history of liver disease, with onset of symptoms within 28 days of the inciting event. Patients may have either a history of acetaminophen overdose (defined as >4 g/day within 7 days of presentation) and/or detectable acetaminophen levels in the serum, with a pattern of liver function tests typical for acetaminophen toxicity (bilirubin < 10 mg/dL and alanine aminotransferase (ALT) ≥ 1000 IU/L), or a diagnosis of hepatitis A, hepatitis B, drug-induced liver injury, autoimmune hepatitis or indeterminate cause based on standard criteria. Standard criteria for these diagnoses are as follows:
 - hepatitis A, defined as positive anti-HAV IgM;
 - hepatitis B, defined as positive anti-HBc IgM and positive HBsAg;
 - autoimmune hepatitis, defined as follows:
 - Globulins elevated $> 1.5X$ ULN;
 - ANA, ASMA or LKMA positive in titer of at least 1:80;
 - Negative serology for viruses associated with acute or chronic hepatitis; and/or

- Liver biopsy showing CAH;
- drug-induced liver injury, defined as presumed injury by a likely agent, with other causes excluded; or
- indeterminate cause, defined as
 - the exclusion of all the diagnoses listed in the Selection Criteria (see Section 6.2), including:
 - Budd-Chiari;
 - Hepatitis C, E, delta, drug-induced hepatitis;
 - mushroom intoxication; and
 - other viruses, defined as follows:
 - HSV: anti-HSV IgM positive and anti-HSV IgG negative and four fold increase between acute and convalescent sera and HSV seen in liver tissue;
 - EBV: anti-EBV IgM or EBV seen in liver tissue; and
 - CMV: anti-CMV IgM positive and anti-CMV IgG negative and four fold increase between acute and convalescent sera or CMV seen in liver tissue.

3. ALI patients may also be enrolled (those meeting the above criteria plus coagulopathy (INR \geq 2.0) and no evidence of encephalopathy).
4. Written informed consent from the patient (ALI) or patient's legally authorized representative or family member if he/she is considered encephalopathic (ALF).
5. Ammonia level \geq 60 μ mol/L at baseline (within 8h prior to T0/initiation of infusion).
6. Serum creatinine levels as follows:
 - a. Cohort 1: Creatinine \leq 1.5 mg/dL; and
 - b. Cohort 2: Creatinine $>$ 1.5 mg/dL and $<$ 10 mg/dL.
7. Mean arterial pressure of $>$ 65 mmHg.

6.2.2 Exclusion Criteria

1. History of chronic liver disease.
2. Signs of overt cerebral herniation, or uncontrolled intracranial hypertension by ICP monitoring (if applicable).
3. Evidence of Wilson's disease, alcoholic hepatitis, biliary obstruction, ischemic hepatitis, severe acute renal tubular necrosis (ATN) due to shock, or any patient with ongoing hypotension.
4. Significant gastrointestinal bleeding (coffee grounds per nasogastric tube and/or melena).
5. Hemodynamic instability, defined by a mean arterial pressure of $<$ 65 mmHg.
6. Cardiopulmonary complications such as pulmonary edema, aspiration pneumonia, heart failure.
7. QT interval of $>$ 500 msec at baseline ECG.
8. Pregnancy.
9. History of malignancy that has not been cured or any cancer in remission for less than 1 year. Non-melanoma skin cancers do not preclude participation in the trial.

10. Concomitant administration of drugs known to interfere with renal excretion of phenylacetylglutamine or those medications that may induce hyperammonemia such as haloperidol, valproic acid and systemic corticosteroids (prohibited during the study). Alternative ammonia modifying agents such as lactulose and rifaximin are not considered standard of care and are prohibited during the study period.
11. Any other health condition that would preclude participation in the study in the judgment of the principal investigator.

6.3 Informed Consent and Enrollment

6.3.1 Informed Consent

The Investigator will select patients in accordance with eligibility criteria detailed in Section 6.2. Prior to the study, for patients with ALF, the patient's legally authorized representative or family member will receive a comprehensive explanation of the proposed treatment including the nature and risks of the study, any known AEs, the investigational status of the components, and the other elements that are part of obtaining proper informed consent. The patient and/or the patient's legally authorized representative or family member will also receive a detailed explanation of the proposed use and disclosure of their protected health information. After having the nature and risks of the study explained to them, the patient and/or the legally authorized representative or family member will be allowed sufficient time to consider participation in the study. Patients who meet criteria for ALI are, by definition, not encephalopathic and will be able to consent for enrollment without additional consents being obtained from a legally authorized representative or family member, although both consents may be obtained.

For those with ALF, the patient's legally authorized representative or family member must provide written informed consent and provide authorization to disclose the patient's protected health information in order to enroll in the study. The informed consent process will be conducted per institutional protocol and in compliance with applicable IRB requirements. Written informed consent must be obtained from the patient's legally authorized representative or family member before any study related activities are conducted. The Investigator must retain all original signed and dated informed consent forms (ICF's) (together with any subsequent IRB-approved amended versions) in the patient's file. A copy of the original signed and dated ICF (and any amendments) must be provided to the patient and/or the patient's legally authorized representative or family member.

If any new information that significantly bears on the patient's risk after receiving the study drug becomes available, the new information will be communicated by the Investigator to the patient and the patient's legally authorized representative or family member. The ICF will be updated and patient's legally authorized representative or family member will be re-consented if necessary (e.g., if patient still in the study and/or local IRB requires re-consent).

6.3.2 Enrollment

Patients will be considered enrolled into the study once informed consent has been obtained, all eligibility criteria are met, and the study drug infusion has been initiated. A study identification number will be assigned by the computer system that houses the study database. A Screen Failure Log will be maintained to capture basic information on all patients screened for the study but who failed to be enrolled. This would include demographic information and the reasons for failure to enroll.

6.3.3 Withdrawal of Consent

The patient or the patient's legally authorized representative or family member is free to withdraw participation in the study at any time and without prejudice to further treatment. The investigator must withdraw any patient from the study if requested. If a patient withdraws consent then no further research data can be collected. Data collected up to the date of the consent withdrawal will be included in the analysis.

6.3.4 Discontinuation of Study Treatment

An Investigator may discontinue a patient's treatment at any time to protect the patient's safety. Reasons that patients may have treatment discontinued include, but are not limited to the following:

- Prolongation of Qt/Qt_c interval of >60 msec over baseline or a Qt/Qt_c interval above 500 msec;
- Evidence of torsades de pointe phenomenon;
- Grade 3 or higher CTCAE toxicity not attributed to acute liver failure in the opinion of the investigator;
- Neutropenia with absolute neutrophil count <500/cumm or platelet count <20,000/cumm, or an increase in serum Cr to a value of >10mg/dL;
- Liver transplantation during the study treatment;
- Withdrawal of informed consent by the patient or patient's legally authorized representative or family member;
- In the case of interruption of infusion for any reason, the study drug will not be restarted if more than 2 hours has elapsed;
- Evidence of shock; and
- Evidence of kidney injury related to study drug will invoke consideration of discontinuation of the study drug.

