1 LIST OF ABBREVIATIONS

Abbreviation	Definition
ACLD	acute on chronic liver disease
AE	adverse event
ALFSG	Acute Liver Failure Study Group
ALF	acute liver failure
ALI	acute liver injury
ALT	alanine aminotransferase (= serum glutamic pyruvic transaminase, SGPT)
ANA	antinuclear antibody
ASMA	anti-smooth muscle AB
AST	aspartate aminotransferase (= serum glutamic oxaloacetic transaminase, SGOT)
ATN	acute renal tubular necrosis
AUC	area under the concentration–time curve
AUC _{0-last}	area under the concentration–time curve from the time of dosing (Time 0) to the time of the last measureable concentration
CAH	chronic autoimmune hepatitis
C _{max}	observed maximum concentration
CMV	cytomegalovirus
Cr	creatinine
CRF	case report form
CTCAE	Common Terminology Criteria for Adverse Events
CVVH	continuous veno-venous hemofiltration
dL	Deciliter
EBV	Epstein-Barr virus
ECG	Electrocardiogram
EDTA	edetic acid (ethylenediaminetetraacetic acid)
FDA	Food and Drug Administration
g	grams
GCP	Good Clinical Practice
h/hrs	hour/hours

Abbreviation	Definition
HAV	Hepatitis A virus
HBc	Hepatitis B core
HBsAg	Hepatitis B surface antigen
HDV	Hepatitis delta virus
HE	hepatic encephalopathy
Hg	mercury
HSV	Herpes simplex virus
ICF	Informed consent form
ICH	International Conference on Harmonization
ICP	intracranial pressure
IgG	Immunoglobulin G
IgM	Immunoglobulin M (antibody)
ICU	Intensive Care Unit
IND	Investigational new drug
IMM	Internal Medical Monitor
INR	International Normalized Ratio (for prothrombin time)
IRB	Institutional Review Board
IU/L	international unit per liter
IV	Intravenous
K3+EDTA	tri-potassium edetic acid (ethylenediaminetetraacetic acid)
LAR	legally authorized representative
LKMA	anti-liver-kidney microsome antibody
µL	Microliter
µmol/L	micromole per liter
MedDRA	Medical Dictionary for Regulatory Activities
mg	milligram
mL	milliliter
mm	millimeter

Abbreviation	Definition
msec	millisecond
MSM	Medical Safety Monitor
MOO	Manual of Operations
NAC	N -acetylcysteine
ng	nasogastric
OCR-002	ornithine phenylacetate
O-log	Orientation Log
PAGN	Phenylacetylglutamine
PCR	polymerase chain reaction (viral diagnostic test)
PD	Pharmacodynamic
PK	Pharmacokinetic
Qt Interval	time from electrocardiogram Q wave to the end of the T wave corresponding to electrical systole
RNA	ribonucleic acid
SAE	serious adverse event
SAR	suspect Adverse Reaction
SDCC	Statistical and Data Coordinating Center
SOP	standard operating procedure
SRC	Safety Review Committee

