Key Exclusion Criteria	
 1. History of chronic liver disease 2. Signs of overt cerebral herniation, or uncontrolled intracranial hypertension by ICP monitoring (if applicable) 3. Evidence of Wilson's disease, alcoholic hepatitis, biliary obstruction, ischemic hepatitis, severe acute renal tubular necrosis (ATN) due to shock, or any patient with ongoing hypotension 4. Significant gastrointestinal bleeding (coffee grounds per ng tube and/or melena) 5. Hemodynamic instability, defined by a mean arterial pressure of <65 mmHg 6. Cardiopulmonary complications such as pulmonary edema, aspiration pneumonia, heart failure 7. QT interval of >500 msec at baseline ECG 8. Pregnancy 9. History of malignancy that has not been cured or any cancer in remission for less than 1 year. Non-melanoma skin cancers do not preclude participation in the trial. 10. Concomitant administration of drugs known to interfere with renal excretion of phenylacetylglutamine or those medications that may induce hyperammonemia

Key Exclusion Criteria Continued	
such as haloperidol, valproic acid and systemic corticosteroids (prohibited during the study). Alternative ammonia modifying agents such as lactulose and rifaximin are not considered standard of care and are prohibited during the study period.
 
11. Any other health condition that would preclude participation in the study in the judgment of the site principal investigator.

Safety Evaluations	
Safety assessments will be performed at:
 
 - Specified time points during the infusion periods (0 to up to 120 h) - At the Completion of the Last Infusion and 24 hours Following the Completion of the Last Infusion - End of study 
During the infusion period, at the Completion of the Last Infusion and 24 hours Following the Completion of the Last Infusion, daily safety assessments will include: abbreviated physical examinations, vital signs (blood pressure, pulse rate, respiration rate, and body temperature), clinical laboratory tests (hematology and serum chemistry), 12-lead ECGs, and reported and observed adverse events.
 
At the Day 30 follow up visit, safety assessments (physical, vitals, hematology/chemistry) including serious adverse events data will be collected.

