*****The ECG at the Baseline visit should be completed prior to the start of the initial study drug infusion.**

8.3 Assessments during Study Treatment

Treatment Day 1 - Time “0” (T0)

Treatment Day 1-T0 is the start of the initial study drug infusion. At this time, each patient will receive an initial infusion rate of OCR-002; thereafter, up and down titration decisions will be based on the patient's tolerance of the study drug infusion, no noteworthy side effects, as well as their Cohort dosing level assignment into the study. The following additional procedures and evaluations are conducted at Treatment Day 1-T0 once the study drug infusion begins:

- OCR-002 Initial Infusion:
Dose Levels 1 through 3: initial infusion rate of 0.139 g/hour for the first 12 hours; continuation at this infusion rate for more than the first 12 hours is dependent on the patient's tolerance of the infusion, no noteworthy side effects, and the patient's Cohort dosing level assignment.
Dose Level 4: initiate infusion rate at the full dose level of 20g/24h (approximately .83g/h) without further dose escalation for a maximum time of 120 hours provided the dose level is well tolerated with no noteworthy side effects.
- Urinalysis*;
*Urinalysis: dipstick plus microscopic evaluation of sediment, if clinically indicated.
- Begin 0-12h urine collection interval;
- Collection of concomitant medications (if applicable);
- Continuous monitoring and collection of mean arterial pressure;
- Continuous monitoring and collection of intracranial pressure (ICP) (if applicable); and
- Begin continuous AE review and reporting.

Each event scheduled for this time point and subsequent time points during the treatment period has a collection window of +/- 3 hours with reference to Treatment Day 1-T0 as time of start of initial study drug infusion, with the exception of ammonia sampling, which has a collection window of +/- 1 hour.

Treatment Day 1 at 6 hrs

- Ammonia collection;
- Collection of concomitant medications (if applicable);
- Continuous monitoring and collection of mean arterial pressure;
- Continuous monitoring and collection of intracranial pressure (ICP) (if applicable);
- Document urine volume; and
- AE review and reporting.

Treatment Day 1 at 12 hrs

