9.8 Safety Assessments

Laboratory Test Results

Blood and urine will be collected at Screening, Baseline (blood only), Treatment Day 1 -T0 (urine only), Treatment Days 1, 2, 3, 4 and 5, at the Completion of the Last Infusion, and 24 hours Following the Completion of the Last Infusion (or Treatment Discontinuation date) for safety laboratory tests to be conducted at local laboratories. Safety assays include:

- Liver function tests (LFTs): Total bilirubin, alkaline phosphatase, alanine aminotransferase (ALT/SGPT), aspartate aminotransferase (AST/SGOT);
- Coagulation: Prothrombin time reported as the international normalized ratio (INR); and
- Urinalysis: dipstick plus microscopic evaluation of sediment if clinically indicated.

Any laboratory test result considered by the investigator to be clinically significant should be considered an AE.

If clinically significant abnormal laboratory values occur during the trial, the patient may be retested regularly until repeat test results return to normal, stabilize, or are no longer clinically significant.

Other Safety Assessments

Vital signs (blood pressure, temperature, heart rate, and respiration) will be measured at Screening, Baseline, Treatment Days 1, 2, 3, 4 and 5, at the Completion of the Last Infusion, and 24 hours Following the Completion of the Last Infusion inclusively. Height will be measured once (at Screening).

Physical examinations will be performed at Screening, Baseline, Treatment Days 1, 2, 3, 4 and 5, at the Completion of the Last Infusion, and 24 hours Following the Completion of the Last Infusion, inclusively (or Treatment Discontinuation Visit).

Single 12-lead ECGs will be performed at Screening, Baseline, Treatment Days 1, 2, 3, 4 and 5, at the Completion of the Last Infusion, and 24 hours Following the Completion of the Last Infusion, inclusively and will be evaluated locally according to usual site procedures.

Inter-current Illness and Pre-Existing Diseases

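### Entry is screened on uncorrected QT alone while QTc above 500 msec is a listed reason to stop, so a patient with a fast heart rate can enter already over that limit; no correction formula is named

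*Combined protocol and SAP*

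**What the plan says.** **Entry.** Exclusion 7 in the Synopsis reads "QT interval of >500 msec at baseline ECG", and Section 6.2.2 has the same criterion. The List of Abbreviations defines the QT interval as "time from electrocardiogram Q wave to the end of the T wave corresponding to electrical systole", which is the measured interval with no rate correction. No entry criterion mentions QTc.

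**Stopping.** Section 6.3.4 lists "Prolongation of Qt/Qt_c interval of >60 msec over baseline or a Qt/Qt_c interval above 500 msec". The list opens with "Reasons that patients may have treatment discontinued include, but are not limited to the following", so it permits discontinuation and does not require it.

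**Measurement.** A pre-dose tracing is already asked for. The footnote to the baseline assessments (Section 8.2) says: "The ECG at the Baseline visit should be completed prior to the start of the initial study drug infusion". Section 9.8 calls for single 12-lead ECGs at each time point, "inclusively and will be evaluated locally according to usual site procedures". Section 11.7.4 summarises ECG intervals and their change from baseline. None of 6.3.4, 9.8 or 11.7.4 names a QTc formula.

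**Background.** Section 3.3.2 reports a dose-related rise in heart rate with modest QT effects in the earlier dose-ranging study. Section 9.1.2 lists tachycardia as expected both with the drug and in the disease.

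**The concern.** The protocol treats QTc as relevant to safety once the drug is running but does not look at it, as a criterion, before the drug starts. Raw QT and QTc agree only at 60 beats/min and separate as the rate rises. A patient with a fast heart rate can therefore satisfy exclusion 7 and, before any drug is given, already have a value that the protocol lists as a reason to consider stopping.

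With no formula named, two of the 6 to 12 sites could also classify the same tracing differently. That affects both limbs of the 6.3.4 item, and it could mix measures in the ECG summaries of 11.7.4.

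The entry screen matters most at Dose Level 4, which starts at the full 20 g/24h. Section 8.3 lists no ECG at T0 or 6 h. The first scheduled on-treatment ECG is at 12 h (window 3 h either way), by which time about 20 × 12/24 = 10 g has been given.

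**Working it through.** The documents state no QTc value, so there is no figure to reproduce. The check asks which raw QT values pass exclusion 7 and still give a QTc above 500 msec.

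**Inputs.** From the documents: the 500 msec entry limit on raw QT, and the 500 msec and >60 msec limits on QT/QTc in 6.3.4. Assumed: heart rates (HR) and QT values, because the documents give no distribution of either, and the formula, because none is named.

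**Formulas** (QT in msec, RR = 60/HR in seconds):
- Bazett: QT × (HR/60)^(1/2)
- Fridericia: QT × (HR/60)^(1/3)
- Framingham: QT + 154 × (1 − RR)
- Hodges: QT + 1.75 × (HR − 60)

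All four equal QT at 60 beats/min and exceed it above 60, so that boundary does not depend on the formula.

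**Raw QT at which QTc reaches 500 msec.** Any QT from just above the tabulated value up to 500 msec passes exclusion 7 with QTc over 500.

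| HR (beats/min) | Bazett | Fridericia | Framingham | Hodges |
|---|---|---|---|---|
| 61 | 496 | 497 | 497 | 498 |
| 70 | 463 | 475 | 478 | 482 |
| 80 | 433 | 454 | 462 | 465 |
| 90 | 408 | 437 | 449 | 448 |
| 100 | 387 | 422 | 438 | 430 |
| 120 | 354 | 397 | 423 | 395 |

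**Examples at 100 beats/min.**
- QT 430: Bazett 430 × 1.2910 = 555; Fridericia 430 × 1.1856 = 510; Framingham 430 + 154 × 0.4 = 492; Hodges 430 + 1.75 × 40 = 500.
- QT 450: 581, 534, 512 and 520 in the same order. All four exceed 500, and the patient is eligible.
- QT 400: 516, 474, 462 and 470. Only Bazett exceeds 500.

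**Band where choosing Bazett or Fridericia decides the answer:** QT 433–454 msec at 80 beats/min (width 21), 408–437 at 90 (width 29) and 387–422 at 100 (width 34).

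**The >60 msec limb.** Suppose QT stays at 400 msec while HR goes from 80 to 110 beats/min:
- Raw QT: change 0.
- Fridericia: 440.3 to 489.6, change +49.
- Bazett: 461.9 to 541.6, change +80.

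Only Bazett crosses 60. Holding QT fixed is a strong assumption. If Fridericia QTc is instead held at 400 msec over the same rise in rate, raw QT falls by 37 and Bazett rises by 23. The measures then disagree in direction, but none reaches 60.

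**Slow rates.** Below 60 beats/min the order reverses. QT 510 msec at 50 beats/min gives Bazett 466 and Fridericia 480. Replacing raw QT by QTc would admit this patient, whom exclusion 7 now bars.

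**The case against.** - **No rule is broken.** Section 6.3.4 is discretionary, and entry and stopping criteria need not use the same measure. This stands, and it is why the point is an improvement to the screen and not a conflict.
- **The investigator can refuse such a patient.** Exclusion 11 covers "Any other health condition that would preclude participation in the study in the judgment of the principal investigator", and the abnormal tracing would be in hand before dosing. This is true, but it sets no QTc value, and an investigator applying exclusion 7 as written has no prompt to calculate one.
- **The slash may mean either measure.** A site that applies raw QT in 6.3.4 has the same 500 msec limit at entry and on treatment. But reading the item as raw QT alone leaves the QTc term with no function, and the doubt is itself part of the gap.
- **Monitoring is dense.** ECGs are scheduled at 12, 24, 36, 48, 72 and 96 h, at the end of infusion and 24 h later, and before each escalation step. Torsades is a separate stopping reason, and heart failure and low arterial pressure are separate exclusions. All of this limits harm after entry but does not change who enters.
- **Earlier data are partly reassuring.** In the dose-ranging study the mean heart-rate rise began at 10 g/4h = 2.5 g/h, against a top rate here of 20 g/24h = 0.83 g/h. That study also gave 3 g/4h (0.75 g/h) and 24-hour infusions of 30 to 60 g (1.25 to 2.5 g/h), with no serious adverse events or discontinuations for adverse events. It concluded that slow infusion avoids peak-concentration effects. This lowers the concern. It does not settle it, because Section 3.3.2 says this is the first study of the drug in acute liver failure.
- **Nothing in the documents favours Fridericia.** This stands. The essential request is one named formula.
- **The case report forms may specify QTc.** They are not among the documents, so the statement about site variation holds for the protocol text only.

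**Conclusion.** The concern holds. The numeric entry screen is weaker than the protocol's own listed stopping value for patients with fast heart rates, and the missing formula leaves the classification of some tracings to site habit. At 100 beats/min the gap covers raw QT of about 387–500 msec by Bazett, 422–500 by Fridericia, 438–500 by Framingham and 430–500 by Hodges. Just above 60 beats/min it is only a few msec wide.

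The existence of the gap rests on the text and on arithmetic and is firm. Its practical frequency cannot be estimated from these documents. The change is worth making because safety is the primary objective and the fix is cheap, but nothing here shows that the trial is unsafe without it.

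**What to change.** 1. In the Synopsis and 6.2.2, change exclusion 7 to *QT or QTc (Fridericia) above 500 msec on the baseline ECG*. Keep the raw QT limit so that entry is not loosened at slow rates; Section 9.1.2 lists bradycardia as well as tachycardia among events expected in this disease.
2. In 6.3.4, keep QT and name the same formula for QTc in both the 500 msec and the >60 msec items. Measure change from the last pre-dose ECG, in line with the baseline definition in 11.6.
3. In 9.8, have sites report QTc by that formula with the heart rate from the same tracing.
4. In 11.7.4, state that QTc summaries use that formula.

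Another formula would also serve if used throughout; the cut-offs move as in the table.

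**Cost.** Wording changes in the Synopsis and four sections, and one value derived from an ECG already required. A case report form or database edit may be needed if QTc and heart rate are not already captured. There may be some extra screen failures among patients with fast heart rates, number unknown. No patient now excluded becomes eligible.
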